Participant Withdrawal. A withdrawal occurs when an enrolled participant actively withdraws consent for further participation in the study, prior to completion of the protocol. Participants may withdraw consent from the trial at any time at their own request, or they may be withdrawn at any time at the discretion of the investigator for safety reasons. All attempts will be made to conduct all evaluations required by the protocol.

Addressing Negative Birth Outcomes. Preterm and negative birth outcomes are common in low income women, especially those with depression who smoke. We will handle these events in the following manner. Women who do not deliver live births will be allowed to continue postpartum treatment if they wish. We will remove them from the sample and replace them with a new participant. For women who experience preterm birth, we will consider providing additional sessions in the postpartum period to ensure a full treatment dose in these individuals. For women who experience other negative birth outcomes which interfere with participation in the postpartum period, we will attempt to make up for missed sessions by increasing the frequency of sessions within the postpartum treatment timeframe. Should negative birth outcomes cause an imbalance in treatment delivery across treatment conditions, this should be detected in our initial analyses of group differences, which will allow us to treat number of treatment sessions as a confounder if such differences are found to be correlated with outcomes (See Statistical Design and Power, Baysesian Modeling Strategy).

Prenatal.

During the prenatal period, participants of 18-22 weeks gestational age will receive 10 individual sessions of BA or HW. The prenatal HW treatment will be similar to the treatment that was utilized in our previous trial.⁵¹ These women will have 16 weeks to complete their 10 individual sessions.

During the prenatal period, participants of 23-32 weeks gestational age will receive 10 individual sessions of BA or HW. The prenatal HW treatment will be similar to the treatment that was utilized in our previous trial.⁵¹ These women will have 12 weeks to complete their 10 individual sessions.

We may do additional check in calls or text communications with participants to maintain engagement between prenatal and postpartum treatment sessions.

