Rate of recruitment will be calculated as the percentage of eligible participants who are consented to participate.

Retention will be calculated as the percentage of enrolled participants who complete the 4 ½ month postpartum assessments.

Completion of treatment visits will be documented using the participant tracking database. These data will be used to calculate the average number of treatment sessions that participants attend and percentage of participants who complete the prenatal and postnatal treatment protocols.

Completion of study measures will be calculated as the percentage of scheduled assessments completed per visit and percentage of scheduled assessments completed per measure.

Rate of receipt of other smoking cessation, psychopharmacological or psychotherapeutic treatment following enrollment will be recorded in the database.

The rate of technical difficulty with smartphone delivery of treatment and assessments will be calculated as the percentage of treatment and assessment sessions that are interrupted due to technical difficulties with the smart phone.

Verification of pregnancy. Participants will confirm positive pregnancy status through study provided pregnancy test or provide paperwork verifying pregnancy status if the pregnancy test is inconclusive.

Biochemical verification of self-report abstinence will be calculated as the ratio of received urine test results (cotinine and/or anabasine) to number of participants who self-reported abstinence at 4 ½ months postpartum

Acceptability of treatment will be assessed in both participants and therapists (see table of assessments for AIM 4) for timepoints. Participants and therapists will be asked to provide ratings of their satisfaction with the BA and HW interventions. Areas that will be included in these ratings are number of treatment sessions, timing of treatment sessions, and quality of interaction with therapists and study staff (for participants' ratings) and quality of interaction with participants (for therapists' ratings).

Therapeutic alliance will be assessed using the client and therapist-rated Working Alliance Inventory, Short Form at PN2, PN4, PN6, PN8, PN10, PP1 & PP3 visits.¹¹⁶ To maintain boundaries in the therapeutic relationship between therapists and the participants with whom they are working, therapists will not be able to access responses or scores on these instruments. In addition, responses on this instrument will be used in data analyses only.

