The PANAS¹²¹, a widely-used 10 item self-report measure of the experience of positive and negative affect within the past week, will be used in Secondary Aim 1 exploratory analyses of hypothesized BA mediators (PA and NA). It will be assessed at baseline and each counseling visit.

The PROMIS Cognitive Function-Abilities (CF-A) Short-form¹²² is from the Patient Reported Outcomes Measurement Information System. This 8-item scale assesses perceived cognitive deficits, including mental acuity, concentration, memory, and perceived changes in these cognitive functions and the extent to which cognitive impairments interfere with daily

functioning. It will be assessed at baseline and each counseling visit. It will be used in Secondary Aim 1 exploratory analyses of hypothesized BA mediators (*cognitive function*).

Nicotine Withdrawal

The Wisconsin Smoking Withdrawal Scale (WSWS)¹²³ This 28 item scale will be used to assess nicotine withdrawal symptoms.

Smoking cessation or depression treatment following enrollment

At each study visit, participants will be asked whether they have started any counseling or medications for the treatment of smoking or depression. These data will be used as covariates in analyses of outcome, as needed.

Additional Measures

Childhood Trauma questionnaire (CTQ). This is a standardized 28-item self-report inventory that measures the severity of five different types of childhood trauma. Approximately 5 minutes is required to complete the questionnaire. A 5-point likert scale is used for the responses from Never true to Very often true.

Medical History. This questionnaire assesses the participants current relevant medical history at the time of the baseline visit.

The Baseline Demographic and Smoking History Form. These questions expand on the data obtained during the pre-screening, providing more detailed information on demographics, information on smoking history (e.g., years smoked, current smoking rate, other nicotine/tobacco use) is also obtained. These questions have been used in our previous and current cessation studies to provide descriptive data for the study population.

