the estimated frequencies, coupled with the low numbers in the control condition we chose to round any fraction for abstinence upward. This had the effect of producing a slightly higher effect in the control condition (n = 3 versus n = 2 abstinent) therefore rendering the simulated effect size more conservative). A fundamental difficulty is that the Frequentist approach cannot provide any indication regarding the relative probability of different values within the 95% Confidence Interval being the true parameter. The Bayesian estimate of the relative risk is slightly different (rounding was necessary in estimating the Frequentist but not the Bayesian solution), RR = 2.73, (95% CI: 0.90-11.44), however since these estimates are based on a posterior distribution it is possible to discuss the probability that an effect of a given magnitude is the governing parameter. Defining benefit as any RR > 1, the simulated posterior distribution shows that there is a 96% chance that the intervention confers this benefit and a more stringent definition (Relative Risk ≥ 1.50) is associated with an 85% probability that intervention confers

benefit. We stipulate that an intervention effect that has at least a 75% probability of increasing the relative risk of abstinence by >1.25 will warrant further investigation in a larger trial. While the above simulation provides a straight-forward example of how Bayesian modeling works, it is often necessary to use more sophisticated Bayesian approaches (e.g., logistic regression with Monte Carlo Markov Chain estimation methods). As such, final analyses will utilize Bayesian generalized linear modeling with multilevel-modeling for repeated measures data.

Bayesian Modeling Strategy Initial analyses examining group differences for baseline variables will use cross-tabulation, ANOVA's, and examination of correlations between baseline variables and specified outcomes. For the purposes of evaluating the comparability of groups, a posterior probability of $\geq 95\%$ will constitute evidence for statistically reliable differences. Baseline or demographic variables on which group differences are detected, and which are correlated with outcomes, meet the definition of confounders^{136, 137} and will result in two sets of analyses: one in which the relevant variable is included as a covariate and one in which it is not. This will permit determination of the degree to which any group differences might confound conclusions regarding treatment.

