
Broadly, the data analytic strategy will use generalized linear and multilevel models (SAS 9.4, R v. 3.5, and Stan 2.17) for both discrete (e.g. smoking abstinence) and continuous (e.g. depression) outcomes.¹³⁸⁻¹⁴⁰ Cross-sectional continuous (depression), dichotomous (smoking abstinence) and time-to-event (retention) data will be evaluated using generalized linear modeling or proportional hazards regression. All analyses will apply intention-to-treat principles with missing imputed as non-abstinent for smoking outcomes. For outcomes other than smoking, Bayesian approaches will implement joint modeling of observed outcomes and the missing data which is robust to ignorable missingness (i.e., MCAR and MAR).¹⁴¹ Sensitivity analyses will evaluate robustness of analytic conclusions to missing data. Non-ignorable missing data patterns will be addressed through pattern-mixture modeling methods.¹⁴² Convergence of Bayesian analyses on the posterior distributions via Monte-Carlo Markov chain (MCMC) will be assessed via graphical (Trace Plot, Autocorrelation Plot) and quantitative (Gelman-Rubin Diagnostics and Effective Sample Size) evidence. Evaluation of posterior distributions will permit statements regarding the probability that effects of varying magnitudes exist, given the data. Specification of diffuse, neutral priors will reflect the initial uncertainty regarding effect sizes. For all generalized linear models, priors for regression coefficients will be specified as \sim Normal ($\mu=0$, $\sigma^2=1 \times 10^4$), level one error variances will be specified as \sim Half-Normal ($\mu=0$, $\sigma^2=1 \times 10^4$). Choice of prior distribution for level two variances will follow Gelman's recommendations.¹⁴³ Bayesian Structural Equation Modeling (**BSEM**) prior specification will adapt recommendations from Muthén and Asparouhov.¹⁴⁴ Priors for the comparison of proportions will be specified as \sim Beta ($\alpha=1.0$, $\beta=1.0$).

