Conduct a preliminary randomized trial with depressed pregnant smokers comparing the BA to HW to evaluate the following: 1) The effect of BA on abstinence at 4 ½ months postpartum, which is a primary outcome. Logistic modeling will evaluate smoking abstinence, measured by biochemically verified TLFB, at 4 ½ months postpartum as a function of treatment group. **2) The effect of BA on depression at 4 ½ months postpartum, which is a primary outcome.** Generalized linear modeling will evaluate depression, measured by the PHQ-9, at 4 ½ months postpartum as a function of treatment group. **3) Feasibility of depressed pregnant smokers' acceptance of the smartphone delivery of BA and HW, and assessment components indicated by a) retention, which is a primary outcome, b) completion of prenatal and postpartum sessions, which is a primary outcome c) completion of study assessments, which is a secondary outcome d) strength of therapeutic alliance from both the participant and therapist perspective, which is a secondary outcome and e) participant and therapist ratings on satisfaction questionnaire, which is a secondary outcome.** Survival analysis will evaluate retention by modeling time to drop-out as a function of treatment condition. Binomial logistic modeling will evaluate the proportion of completed sessions as a function of treatment condition across the entire study as well as in the pre-natal and post-partum periods separately. Generalized linear models will evaluate participant and clinician measures of therapeutic alliance, measured by the WAI, as a function of treatment group. Similarly, generalized linear modeling will evaluate satisfaction as a function of treatment group. **4) Feasibility of study procedures as indicated by a) percentage of sessions interrupted by technical difficulties, which is a secondary outcome, and b) percentage of urine tests (cotinine and/or anabasine) received for biochemical verification of self-reported abstinence at 4 ½ months postpartum follow-up, which is a secondary outcome.** Binomial logistic models will evaluate the proportion of sessions interrupted for technical difficulties and the proportion of biochemically verified abstinence measures as a function of treatment. These analyses will provide estimates with 95% credible intervals for each of these proportions in each group that will permit assessment of feasibility.

Specific Analyses: Secondary Aim 1 (Stage IB)

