As outlined in the Safety Monitoring Protocol and Procedures (see Appendix), we will evaluating and assessing the severity of depressive and anxiety symptoms, other psychiatric disorders as well as suicide risk, using information from the PHQ-9, C-SSRS, and MINI administered at screening (AIM 1), and the PHQ-9, C-SSRS, MINI and Generalized Anxiety Disorder – 7 (GAD-7), administered at screening (AIM 3 & Aim 4). Additionally, we will be assessing for depressive and anxiety symptoms and suicide risk at the counseling sessions throughout treatment and have outlined procedures for monitoring changes of these symptoms and ideations (Appendix Safety Monitoring Plan). The document also outlines procedures for addressing other mental health concerns, reporting of elder or child abuse and neglect, domestic/intimate partner violence and crises that occur during sessions.

Participants who are rated on the Columbia-Suicide Severity Rating Scale at screening as having active suicidal ideation with some intent to act and active suicidal ideation with specific plan and intent, who fall within the extremely severe range of depressive symptom severity, who endorse having severe vegetative symptoms, bipolar symptoms, psychotic symptoms, or who are experiencing symptoms associated with Axis I disorders that place them at risk of harm will be further evaluated by a designated Master's or Ph.D. level Mental Health Professional (MHP) to make an appropriate treatment disposition. When needed, participants will be referred to collaborators at The University of Texas Health Science Center (UTH) to manage the action plan/treatment interventions as they deem appropriate or provided with outside referral(s).

Vulnerable Subjects

There is no additional risk to pregnant women and their fetuses posed by participation in the study. The intervention seeks to reduce smoking and depression in women in both the prenatal and postpartum period. Reduction in smoking and depression during these periods may benefit both the woman, the fetus and the neonate.

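### Outside smoking or depression treatment started after enrolment may be entered as an outcome covariate with no stated rule; this changes the estimand and can bias the BA effect in either direction

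*Combined protocol and SAP*

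**What the plan says.** The subsection on smoking cessation or depression treatment following enrollment (AIM 3 and AIM 4 Assessments) defines the variable: "At each study visit, participants will be asked whether they have started any counseling or medications for the treatment of smoking or depression". It then gives its use: "These data will be used as covariates in analyses of outcome, as needed".

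Other parts of the plan bear on this:

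- **Feasibility Measures: AIM 4** treats the same information as a rate: "Rate of receipt of other smoking cessation, psychopharmacological or psychotherapeutic treatment following enrollment will be recorded in the database".
- **Bayesian Modeling Strategy** has a covariate rule with paired analyses, with and without the covariate. Its scope is limited: "Baseline or demographic variables on which group differences are detected, and which are correlated with outcomes, meet the definition of confounders".
- The same section states the analysis principle: "All analyses will apply intention-to-treat principles with missing imputed as non-abstinent for smoking outcomes".
- **Specific Data Analyses: Aim 4** writes the depression model on arm alone: "Generalized linear modeling will evaluate depression, measured by the PHQ-9, at 4 ½ months postpartum as a function of treatment group". The logistic model for abstinence is written the same way.
- **Addressing Negative Birth Outcomes** brings in another post-randomisation variable, the session count, "which will allow us to treat number of treatment sessions as a confounder if such differences are found to be correlated with outcomes".

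**The concern.** Randomisation makes the arms comparable on what precedes assignment. Treatment begun later can be a consequence of assignment. The plan's theoretical model expects BA to improve affective states more than HW does, and mood is followed during treatment: "we will be assessing for depressive and anxiety symptoms and suicide risk at the counseling sessions throughout treatment". Women in individual psychotherapy at entry are excluded from Aim 4, so any individual psychotherapy recorded later began after entry. A path from arm to mood to outside treatment is therefore plausible, with mood also acting on the outcome.

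If so, outside treatment is partly a marker of poor course and partly an effect of arm. Conditioning on it changes the question from the effect of being assigned to BA to something with no clear causal meaning. Because the plan leaves its use to need, the choice could be made once uptake by arm is visible. In a small trial, chance imbalance alone could make adjustment look necessary. The trial exists to supply effect sizes for planning a larger one, so what the estimate means should be fixed beforehand.

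**Working it through.** **1. The plan's own figure.** The Simulated Example uses Beta(3.28, 28.72) for control and Beta(8.5, 23.5) for intervention. Two million draws give a median RR of 2.75 (95% interval 0.90 to 11.47), P(RR > 1) = 96.2% and P(RR ≥ 1.5) = 84.9%. The plan states 2.73 (0.90 to 11.44), 96% and 85%. For 8/30 v 3/30, Fisher's p is 0.181 and RR = (8/30)/(3/30) = 2.67, with interval exp[ln 2.67 ± 1.96 √(1/8 − 1/30 + 1/3 − 1/30)] = 0.78 to 9.09, as stated. The example reproduces. It contains no covariate, so it does not show what adjustment would do.

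**2. Simulation for PHQ-9.** Every input here is an assumption, since the documents give none: BA lowers mid-study PHQ-9 by 3 points, mood SD is 5, residual SD is 3, and 30% of women start outside treatment T. The log-odds of T per PHQ-9 point run from 0 to 0.5, and the true benefit of T from 0 to 8 points. Large samples (400,000) isolate bias from noise. The model with arm alone is compared with arm plus T. Selected settings:

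| Log-odds per point | True benefit of T | Uptake BA / HW | Arm alone | Arm + T | Coefficient of T | Ratio |
|---|---|---|---|---|---|---|
| 0 | 4 | 30.0% / 29.9% | −3.05 | −3.05 | −4.0 | 1.00 |
| 0.10 | 0 | 26.9% / 32.9% | −2.97 | −2.82 | +2.4 | 0.95 |
| 0.50 | 0 | 21.8% / 38.3% | −2.99 | −1.87 | +6.8 | 0.62 |
| 0.25 | 0 | 23.7% / 36.0% | −3.01 | −2.40 | +4.9 | 0.80 |
| 0.25 | 2 | 23.9% / 36.2% | −2.74 | −2.39 | +2.9 | 0.87 |
| 0.25 | 6 | 23.9% / 36.2% | −2.27 | −2.41 | −1.1 | 1.06 |
| 0.25 | 8 | 24.0% / 36.2% | −2.01 | −2.39 | −3.1 | 1.19 |

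Over all settings where mood drives uptake, the ratio is 0.62–0.95 with no benefit, 0.70–0.99 with 2 points, 0.80–1.04 with 4, 0.93–1.09 with 6 and 1.12–1.19 with 8. If BA itself also prompts outside treatment (+0.7 log-odds), the ratio is 0.84–1.06 for benefits of 0 to 4 points.

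**3. Why the sign varies.** For least squares, arm alone = adjusted + (coefficient of T) × (uptake in BA − uptake in HW). With no benefit: −2.399 + 4.909 × (0.237 − 0.360) = −3.00. With an 8-point benefit: −2.385 − 3.100 × (0.240 − 0.362) = −2.01. The sign of the coefficient sets the direction. That coefficient mixes the true benefit with worse mood among users, so T can look harmful or helpful whatever it does. Nor does the adjusted figure recover the BA effect with no outside treatment. That effect is −3.0 by construction here, while the adjusted values run from −1.85 to −2.87 when mood alone drives uptake.

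**4. Abstinence.** Anchored at the plan's 7.6% and 25%, the unadjusted RR is 25/7.6 = 3.29. With mood acting on abstinence (assumed −0.2 log-odds per point), the adjusted standardised RR is 2.84–3.22 if T has no benefit. It is 3.54–3.69 if T adds 2.1 log-odds.

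**5. Size against noise.** With an assumed SD of 6, the SE of the PHQ-9 difference is 6√(2/25) = 1.70 at N = 50 and 6√(2/30) = 1.55 at N = 60. The largest shift toward the null is 2.99 − 1.87 = 1.12 points, and the largest away is 2.39 − 2.01 = 0.38. Both are below one SE.

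**6. The go-forward rule.** The rule asks for at least 75% probability that RR exceeds 1.25. With Beta(1, 1) priors and 7.6% v 25%, that probability is 89% at N = 50 and 91% at N = 60. Taking the lowest adjusted RR, 2.84 × 7.6% = 21.6% in BA, it falls to 83% and 86%.

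**The case against.** The strongest reply is that the covariate sentence sits in a list of measures, while the section that specifies the analyses writes both primary models on treatment group alone. On that reading the sentence permits adjustment somewhere and does not prescribe it for the primary analysis. This stands: a reader might infer that the primary estimates will be adjusted, or that the choice will be made after looking at the data, and the documents state neither. But the sentence speaks of outcome analyses without limit, and nothing confines it to supplementary work.

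Second, intention to treat concerns who is analysed and in which arm, and a covariate moves nobody. This also stands, so it goes too far to say that the sentence breaks the randomised comparison outright. The tension is with the estimand that the principle implies.

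Third, the causal path is plausible but not shown. The explicit referral text in the safety monitoring section concerns findings at screening, and the in-treatment procedures are in an appendix not reproduced here. No uptake is reported. Women in other cessation treatment who refuse to refrain are excluded, which may hold down part of the variable. If uptake were unrelated to arm and mood, adjustment would do almost nothing (ratio about 1.0).

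Fourth, the bias is modest beside the sampling error of a pilot. That is so, and it limits the severity. It gives no reason to leave the model open.

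**Conclusion.** The point holds as a specification gap with a possible bias of unpredictable sign. The plan allows conditioning on a variable measured after randomisation, without trigger, coding or status. The paired with-and-without safeguard does not reach it, because that rule covers baseline or demographic variables only.

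A reader might go further and conclude that adjustment must shrink a real BA effect, or that outside treatment must look harmful. The documents support neither. With weak or modest benefit the shift is mostly toward the null. With strong benefit and more use in HW it goes the other way, and the apparent effect of outside treatment can take either sign. Nor is there support for saying that the go-forward decision would change: at the planned rates it does not.

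All the magnitudes rest on the assumed uptake, mood dependence and benefit. What does not rest on them is that an adjusted estimate is no longer the effect of assignment. This should be corrected, but as a matter of wording.

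**What to change.** Replace the covariate sentence in the measures section with text to this effect:

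> The primary abstinence and PHQ-9 analyses compare women as randomised, regardless of treatment started after enrolment, and include no post-randomisation covariates. Receipt of outside treatment is reported by arm. Any analysis that accounts for it is pre-specified and labelled supplementary.

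State in the Bayesian Modeling Strategy that covariates are limited to variables measured before randomisation. The session-count provision under negative birth outcomes conflicts with that rule and should be reconciled with it in the same edit. The feasibility section already records the rate of outside treatment, so only the breakdown by arm needs adding.

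If the effect in the absence of outside treatment is of interest, an optional PHQ-9 sensitivity analysis could handle scores after its start as missing in the longitudinal model, with the assumptions stated. The same device should not be used for abstinence, because the plan counts missing smoking outcomes as non-abstinent.

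The cost is a few sentences, with no new data, visits or measures.
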